### Analysis of Secondary Endpoints

The degree of response will be summarized. Among eligible patients who achieve CR/CRh, disease-free survival (DFS) will be calculated. DFS is defined from the date of first CR/CRh until the first date of relapse/progression or death from any cause. Any patient without progression or death will be censored at the last date of clinical assessment. Further, patients who go to transplant prior to a progression will be censored at that time. The number and proportion of patients going to transplant prior to progression will be provided. Overall survival (OS) will be calculated for all eligible patients who start therapy. OS will be defined from the treatment start date until the date of death from any cause or date last known alive. Both time-to-event endpoints will be summarized by the Kaplan-Meier method. Associations between baseline variables and clinical outcome will be descriptive in nature due to the small sample sizes, primarily using

graphical displays to identify patterns and trends.

The maximum grade of each type of adverse event will be recorded for each patient and summarized. Treatment-related adverse events, defined as possibly, probably or definitely related to study treatment per NCI CTCAE v5.0 will be summarized separately. In addition, reasons for treatment discontinuation and number of TP-0903 cycles received will be summarized and used to assess tolerability. All patients who have received at least one dose of study drug will be evaluable for safety and tolerability assessments.

Initial analysis of plasma PK data will include standard compartmental and non-compartmental methods using Phoenix WinNonlin version 6.3 to generate estimates for relevant parameters (CL/F, V/F, Cmax, t1/2, AUC, etc.). Descriptive statistics will include means, standard deviations, and frequencies will be computed for all variables. Relationships between continuous variables will be performed using standard linear correlation and linear regression. Relationships between PK parameters such as Cmax and AUC with response will be performed using standard t-tests or Wilcoxon rank sum tests and illustrated using boxplots or other graphical displays. Differences in cytokines/chemokines, kinase signaling, and gene expression between days 1 and 5 will be evaluated using paired t-tests or Wilcoxon signed rank tests. Values will be log transformed as appropriate to reflect biologic plausibility. Patterns of sensitivity and resistance will be purely descriptive.

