### **5.2.3. Severity**

Definitions found in the Common Terminology Criteria for Adverse Events version 5.0 (CTCAE v5.0) will be used for grading the severity (intensity) of AEs. The CTCAE v5.0 displays Grades 1 through 5 with unique clinical descriptions of severity for each referenced AE. Should a patient experience any AE not listed in the CTCAE v5.0, the following grading system should be used to assess severity:

- Grade 1 (Mild AE) – experiences which are usually transient, requiring no special treatment, and not interfering with the patient's daily activities
- Grade 2 (Moderate AE) – experiences which introduce some level of inconvenience or concern to the patient, and which may interfere with daily activities, but are usually ameliorated by simple therapeutic measures
- Grade 3 (Severe AE) – experiences which are unacceptable or intolerable, significantly interrupt the patient's usual daily activity, and require systemic drug therapy or other treatment
- Grade 4 (Life-threatening or disabling AE) – experiences which cause the patient to be in imminent danger of death
- Grade 5 (Death related to AE) – experiences which result in patient death

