### **5.3.2. Assessment of Adverse Events**

Investigators will assess the occurrence of AEs and SAEs at all patient evaluation time points during the study. All AEs and SAEs whether volunteered by the patient, discovered by study personnel during questioning, or detected through physical examination, clinically significant laboratory test, or other means will be recorded in the patient’s medical record and on the AE CRF and, when applicable, on an SAE/Event reporting form.

Each recorded AE or SAE will be described by its duration (i.e., start and end dates), severity, regulatory seriousness criteria, if applicable, suspected relationship to the investigational product (see following guidance), and any actions taken.

All deaths should be reported with the primary cause of death as the AE term, as death is typically the outcome of the event, not the event itself. The primary cause of death on the autopsy report should be the term reported.

An SAE will qualify for expedited reporting to regulatory authorities if the SAE is considered a Suspected Adverse Reaction and is not listed in the current Investigator’s Brochure (i.e., an unexpected event). To ensure consistency of AE and SAE causality assessments, investigators should apply the following general guideline:

Fatal	Adverse event resulted in death.
--------------	----------------------------------

Unrelated	Another cause of the adverse event is more plausible; a temporal sequence cannot be established with the onset of the adverse event and administration of the investigational product; or, a causal relationship is considered biologically implausible.
Possibly Related	There is a clinically plausible time sequence between onset of the adverse event and administration of the investigational product, but the adverse event could also be attributed to concurrent or underlying disease, or the use of other drugs or procedures. Possibly related should be used when the investigational product is one of several biologically plausible adverse event causes.
Definitely Related	The adverse event is clearly related to use of the investigational product.

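### The causality guideline in Section 5.3.2 lists Fatal as a level and does not match Section 10, so a drug-related death could be missed in the treatment-related summary if one level is chosen per event

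*Combined protocol and SAP*

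**What the plan says.** Section 5.3.2 requires each recorded AE or SAE to be described by several items, one of which is the "suspected relationship to the investigational product (see following guidance". The guidance is introduced with the words "To ensure consistency of AE and SAE causality assessments, investigators should apply the following general guideline" and has four levels:

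- **Fatal**, defined only as "Adverse event resulted in death".
- **Unrelated**, whose definition begins "Another cause of the adverse event is more plausible".
- **Possibly Related**, which ends with the instruction "Possibly related should be used when the investigational product is one of several biologically plausible adverse event causes".
- The last level, **Definitely Related**, is reserved for events with a clear link to the study drug.

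There is no Probably level.

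Section 10 (Analysis of Secondary Endpoints) plans two adverse event summaries. The first takes each patient's worst grade for each event type, whatever the cause. The second is restricted to treatment-related events, "defined as possibly, probably or definitely related to study treatment per NCI CTCAE v5.0". The safety set is everyone who received any study drug.

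Death is already captured in two other places. Section 5.2.3 gives Grade 5 to "experiences which result in patient death", and Section 5.2.2 makes a fatal result a criterion for seriousness.

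**The concern.** A relationship scale should answer one question: did the drug cause the event? Fatal answers a different one, namely how the event ended. A death can be drug-related or not, so Fatal overlaps every other level, and neither section says how the analysis should classify it. Section 10 then counts a level that investigators are never offered (Probably) and is silent on one that they are (Fatal).

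The toxicity profile is a secondary objective. At stake is whether a death that the investigator thinks was caused by TP-0903 appears in the summary meant to show treatment-related events. Section 10 also credits its scale to CTCAE v5.0. Elsewhere the protocol uses CTCAE to characterise and grade toxicities (Sections 4.1 and 5.2.3), so the citation does not tell the reader which relationship scale applies.

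**Working it through.** The plan gives no figure to reproduce. The check sets the two lists of levels side by side.

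| Level | In Section 5.3.2 | In Section 10's related set | Result |
|---|---|---|---|
| Fatal | Yes, with no statement on cause | No | Neither related nor unrelated |
| Unrelated | Yes | No | Not related, as intended |
| Possibly | Yes | Yes | Related |
| Probably | No | Yes | Never used |
| Definitely | Yes | Yes | Related |

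**Probably.** The related levels that investigators can choose are Possibly and Definitely, and Section 10 counts both. An event that might have been called probable goes to one of these two and is counted. The Probably cell stays empty and nothing is lost.

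**Fatal.** Take a death that the investigator believes was drug-related. The result depends on how the table is used:

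1. One level is chosen and it is Fatal. No relatedness is recorded, Section 10's definition is not met, and the death is missing from the treatment-related summary.
2. One level is chosen and it is Possibly or Definitely. The death is counted.
3. Fatal is recorded together with a relationship level. The death is counted.

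In all three cases the death appears in the all-cause summary as Grade 5. Only case 1 loses anything, and only from the treatment-related summary.

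**Size of one misplaced death.** The denominator is all dosed patients. The Accrual subsection of Section 10 plans 40 to 46 patients. If all are dosed:

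- 1/40 = 2.5%
- 1/46 = 2.2%

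If the trial stopped at the interim analysis and only its 13 patients had been dosed, the figure would be 1/13 = 7.7%. These percentages show the weight of a single event. They do not estimate how often miscoding would occur.

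**The case against.** The strongest reply is that the protocol already expects a relatedness judgement for every event. Section 5.3.2 lists the suspected relationship as a required item separate from severity and seriousness. It calls the table a general guideline, and nothing says that only one row may be chosen. Section 5.5 sets a seven-day limit for unexpected suspected reactions that are fatal or life-threatening, which presupposes that a death can be rated for cause. No CRF is included in the documents. In the text available, the Fatal row stands apart from the other three, so it may have been laid out separately. This all stands, and it is why the loss can be stated only conditionally. It does not remove the defect: the required relationship item is still referred to this table, the introductory sentence covers the Fatal row, and no text says that Fatal must be accompanied by a relationship level.

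Three stronger readings are tempting, and the documents do not support them:

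- *Every death coded under the guideline loses its relatedness.* This assumes single-choice coding, which the documents leave open.
- *The missing Probably level helps events to drop out.* It does not, because both available related levels are counted.
- *Expedited reports would be missed.* Section 5.2.4 defines a suspected adverse reaction by reasonable possibility, with its own criteria, and Section 5.5 sends every SAE to the IRB within 24 hours whatever its cause. No reporting duty can be shown to fail.

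**Conclusion.** The two sections do not match, and Fatal does not belong on a relationship scale. The consequence is limited and conditional: a drug-related death is absent from the treatment-related summary only if one level is chosen per event and that level is Fatal. It remains in the all-cause summary. The Probably mismatch is a matter of labelling.

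One misplaced death would be about 2.2% to 2.5% of the safety set, assuming that 40 to 46 patients are enrolled and all are dosed. A reader might divide by 31 instead, but that is the number evaluable for the efficacy decision, not the safety set that Section 10 defines.

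This is a minor point. It does not affect the primary endpoint, the two-stage design or the sample size. It is still worth correcting, because the ambiguity falls on deaths, where a single event matters in a trial of this size.

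**What to change.** - Remove Fatal from the guideline in Section 5.3.2, and record death as Grade 5 and as an outcome. Nothing is lost, because grade and seriousness already capture it.
- State that every AE and SAE must have a relationship level, including Grade 5 events.
- Use one set of relationship levels in Sections 5.3.2 and 10: either define Probably in Section 5.3.2 or delete it from Section 10. State that every event rated possibly related or higher enters the treatment-related summary.
- Remove the attribution of that scale to CTCAE v5.0, and refer to Section 5.3.2 instead.

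The cost is a wording change in two sections and possibly one CRF field. If any deaths have already been coded Fatal without a relationship level, the investigator should add one before the safety tables are produced.

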## **11. Ethics and Regulatory Requirements**

### **11.1. Patient Protection**

This study will be conducted according to the principles outlined by the Declaration of Helsinki and all applicable amendments; the International Conference of Harmonization 29 Version 05/21/2013 (ICH) Guidelines for Good Clinical Practice; the U.S. Food and Drug Administration (FDA) regulations regarding the conduct of clinical trials and the protection of human subjects; the Institutional Review Board (IRB), any applicable local health authority, and the Ethics Committee requirements.

### **11.2. Patient Information**

Before entry into the trial all eligible patients will receive written patient information describing the aim of the study, as well as probable and possible side effects and risks. Oral information from one of the investigators or a delegated person at the institution will also be given, and the patient must have the opportunity to ask questions, and to consider participation together with his/her family members if applicable. It will be emphasized that the participation is voluntary and that it is the right of the patient to refuse further participation in the study whenever he/she wants and that this will not influence his/her subsequent care.

### **11.3. Informed Consent**

Patient / Legally acceptable representative (LAR) (as applicable) written consent must be obtained according to local Institutional and/or University Human Experimentation Committee requirements and must conform to the ICH guidelines for Good Clinical Practice, prior to any study-specific screening procedures and trial entry. The written informed consent form should be signed and personally dated by the patient or by the patient's legally acceptable representative. A copy of the signed informed consent will be given to the patient or patient's legally authorized representative. The original signed consent must be maintained by the investigator at OSU available for inspection by the sponsor, or regulatory authority

at any time. The IRB will review the consent form for approval.

#### **11.4. Ethics Board Approval**

This study must obtain the approval of the protocol, the informed consent document and any other material used to inform the patient about the nature of the trial by a properly constituted IRB. The trial should not start until a copy of this written approval has been received by the Investigator. The Investigator will supply with a copy of the IRB approval letter stating that the study protocol and any subsequent amendments and informed consent have been reviewed and approved. The investigator or designee will be responsible for obtaining annual IRB re-approval throughout the duration of the study including at completion or termination.

Any changes to this protocol made by the Investigator must be in the form of a written amendment and the amendment will be appended to the protocol. Approval of amendments by the IRB is required prior to their implementation, unless there are overriding safety reasons.

Upon completion of the trial, the Investigator must provide the IRB and sponsor with a summary of the trial's outcome.

Annual Report: The PI will submit annual reports to the sponsor and FDA.

### **12. Documentation, Record Access and Maintenance of Study Records**

#### **12.1. Documentation of Patient's Participation**

A statement acknowledging the participation of a patient in this clinical trial must be documented in the patient's medical records along with the signed ICF.

#### **12.2. Source Documentation**

Source records are original documents, data, and records (e.g., medical records, raw data collection forms, pharmacy dispensing records, recorded data from automated instruments, laboratory data) that are relevant to the clinical trial. The Investigator will prepare and maintain adequate and accurate source documents. These documents are designed to record all observations and other pertinent data for each patient enrolled in this clinical trial. Source records must be adequate to reconstruct all data transcribed onto the Case Report Forms (CRFs).

#### **12.3. Regulatory Requirements**

Before the investigational drug is shipped to the Investigator, the Investigator will provide to the sponsor with a copy of the IRB approval letter stating that the study protocol and any subsequent amendments and informed consent form have been reviewed and approved.

#### **12.4. Patient Confidentiality and Access to Source Data/Documents**

##### **12.4.1. Patient Identification**

A sequential unique identification number will be attributed to each patient registered in the trial. This number will identify the patient and must be included on all case report forms. A patient will not be identified by name, only by his/her initials. The patient's name or any identifying information will not appear in any reports published as a result of this study. In order to avoid identification errors, patient's initials and date of birth (as permitted by the ethics board) will also be reported on the study forms. Any

research information obtained about the patient in this study will be kept confidential. However, information obtained from individual patient's participation in the study may be disclosed with his/her consent to the health care providers for the purpose of obtaining appropriate medical care. The patient's medical records/charts, tests will be made available to the sponsor Sumitomo Dainippon Pharma Oncology, Inc. (SDPO), the US FDA, and the IRB and any other regulatory authorities. This is for the purpose of verifying information obtained for this study. Confidentiality will be maintained throughout the study within the limits of the law.

A patient's name will not be given to anyone except the researchers conducting the study, who have pledged an oath of confidentiality. All identifying information will be kept behind locked doors, under the supervision of the study Principal Investigator and will not be transferred outside of the hospital.

A patient may take away his/her permission to collect, use and share information about him/her at any time. If this situation occurs, the patient will not be able to remain in the study. No new information that identifies the patient will be gathered after that date. However, the information about the patient that has already been gathered and transferred may still be used and given to others as described above in order to preserve the scientific integrity and quality of the study.

#### **12.5. Confidentiality of the Study**

Data generated as a result of this study are to be available for inspection on request by local health authority auditors, the Sponsor's Study Monitors and other personnel (as appropriate) and by the IRB. The Investigator shall permit sponsor, authorized agents of the sponsor, and regulatory agency employees to enter and inspect any site where the drug or records pertaining to the drug are held, and to inspect all source documents. The protocol and other study documents contain confidential information and should not be shared or distributed without the prior written permission of sponsor.

Release of research results should preserve the privacy of medical information and must be carried out in accordance with Department of Health and Human Services Standards for Privacy of Individually Identifiable Health Information, 45 CFR 164.508.

#### **12.6. Registration of Clinical Trial**

Prior to the first patient being registered/enrolled into this study, the Sponsor will be responsible for ensuring that the clinical trial is registered appropriately to remain eligible for publication in any major peer-reviewed journal, adhering to the guidelines put forth by the International Committee of Medical Journal Editors (ICMJE).

#### **12.7. Maintenance of Study Records**

To enable evaluations and/or audits from Regulatory Authorities, the Investigator agrees to keep records, including the identity of all participating patients (sufficient information to link records, CRFs and hospital records), all original signed informed consent forms, copies of all CRFs, source documents, and detailed records of treatment disposition.

According to 21 CFR 312.62(c), the Investigators shall retain records required to be maintained under this part for a period of two years following the date a marketing application is approved for the drug for the indication for which it is being investigated. If no application is to be filed or if the application is not approved for such indication, the Investigator shall retain these records until two years after the

investigation is discontinued and the FDA is notified. The Investigator must retain protocols, amendments, IRB approvals, copies of the Form FDA 1572, signed and dated consent forms, medical records, case report forms, drug accountability records, all correspondence, and any other documents pertaining to the conduct of the study.

If the investigator relocates, retires, or for any reason withdraws from the study, then the Sponsor should be prospectively notified. The study records must be transferred to an acceptable designee, such as another investigator, another institution, or to the Sponsor. The investigator must obtain the Sponsor's written permission before disposing of any records.

### **13. Administrative Procedures**

#### **13.1. Protocol Deviations and Violations**

All violations or deviations are to be reported to the site's IRB (as per the ethics board's guidelines). All IRB correspondence is to be forwarded to the sponsor. The site must notify the sponsor immediately of any protocol violations.

#### **13.2. Premature Discontinuation of the Study**

The Sponsor reserves the right to discontinue the trial for any reason but intends only to exercise this right for valid scientific or administrative reasons. After such a decision, the Investigators must contact all participating patients immediately after notification. Standard therapy and follow-up for patients will be assured and, where required by the applicable regulatory requirement(s), the relevant regulatory authority(ies) will be informed.

The IRB will be informed promptly and provided with a detailed written explanation for the termination or suspension.

As directed by the Sponsor, all study materials must be collected and all CRFs completed to the greatest extent possible in the case of a premature discontinuation of study.

## Appendix A. Cytochrome P450 Drug Interaction Table

Physicians should be aware of the possibility of drug interactions when TP-0903 is co-administered with drugs that are inhibitors or inducers of CYP2C19. Physicians should refer to the products label and to the drug interaction website provided below. The website listing Cytochrome P450 inhibitors and inducers is updated on an ongoing basis and can be found at <http://medicine.iupui.edu/clinpharm/ddis/main-table>. Below is a snapshot of the website as of August 2018. **Attention should be focused on the 2C19 column.** Please note that the website also lists substrates of CYP2C19.

